## 4 Sample Size Requirements

Up to 500 subjects are considered a meaningful sample size to assess real-world use of the MANTA device. There is no statistical basis for the sample size. Up to 20 sites will be included in the trial.

## 5 Statistical Analyses and Study Objectives

Statistical analyses will consist of descriptive statistics mean, standard deviation, median, minimum/maximum and 95% confidence intervals for continuous data and counts, proportions and 95%

confidence intervals for categorical data. Data will be qualitatively compared to VARC-2 endpoints in the literature.

All subjects with an attempted procedure where femoral artery access was initiated and MANTA device was attempted will be included in the performance and safety measures. The performance and safety endpoints will be summarized for the overall population, by cohort (TAVR vs not TAVR), and by MANTA device size (14 or 18 Fr) at a minimum. The 12M safety endpoint will also be summarized for the 12M cohort.

At the time this SAP was drafted, enrollment has closed, but follow-ups are still being completed. One subject had both sides (left and right femoral arteries) used for procedures of all enrolled subjects so summaries may be either patient based (number of participants) or device based (number of participants + 1).

The protocol specified that results will be compared to values observed in the literature. This comparison can be made by comparing the 95% confidence intervals to rates from literature. If the rate is within the 95% confidence interval, the prespecified intention is to report that a difference between the prior literature reported rate and the MARVEL study's observed rate has not been demonstrated. At a minimum, the results will be compared to the observed rates from the 2 pre-market trials, the EU Pre-Market Clinical Study (Netherlands and Italy, N=50) and the U.S. Pivotal trial (N=263 primary analysis cohort).

**Table 2.** Rates from pre-market trials for MANTA device

Trial	Time to Hemostasis (min) Mean $\pm$ SD, Median, Range, upper 97.5% confidence bound	Major Complication Rate (%) percent, 97.5% upper confidence bound	Major VARC-2 Complication Rate (%) percent	Minor Complication Rate (%) percent
EU Pre-market study (N=50)	2.38 $\pm$ 6.63 0.4 Range: 0, 37 97.5% UCB = N/A	3/50 (6%)	1/50 (2%)	0/50 (0%)
FDA PMA results (N=263)	1.09 $\pm$ 2.63 0.4 97.5% UCB = 1.41	5.3% 97.5% UCB = 8.8%	4.2%	2.7%

Additional VARC-2 complication rates have been pulled from the literature and are summarized in Table 3 below.

**Table 3.** Rates of major and minor VARC-2 complication rates from Literature Review Update PSD-281, Rev A, 07 Feb 2019, prepared by Essential Medical, a wholly owned subsidiary of Teleflex.

Article	VCD	N	Major VARC2 (%)	Minor VARC2 (%)	Weighted Major VARC2 (%)	Weighted Minor VARC2 (%)
Biancari	MANTA	107	9.3	3.7		
Moriyama	MANTA	111	7	6		
De Palma	MANTA	89	1.1	4.6		
Mach	Perclose (assorted)	466	6	14.4	6	14.4
Moriyama	Proglide	111	8	13		
Honda	Proglide x1 + echo	63	1.6	19.1		
Sorropago	Proglide x1 + glue	250	0	1.6		
	Proglide x1 or x2	58	17.2	15.5		
Biancari	Proglide x2	115	12.2	2.6		
Mas-Peiro	Proglide x2	100	2	4		
Veulemens	Prostar	389	1.2	12.3		
Kochman	Prostar	203	6.9	18.2		
Lareyre	Prostar	340	1.8	25.5		
De Palma	Prostar	257	1.9	2.7		
Overall (weighted)		2659	4.2	11.5		

## 5.1 Performance Endpoint: Time to Hemostasis

Objective: To quantify the real-world time to hemostasis using the MANTA devices.

Endpoint: time to hemostasis defined as the elapsed time between MANTA deployment (withdrawal of sheath from artery) and first observed and confirmed arterial hemostasis (no or minimal subcutaneous oozing and the absence of expanding or developing hematoma). Exact time collected and reported on Artery Assessment and Procedure electronic Case Report Forms (eCRFs).

Hemostasis success is defined as hemostasis at the puncture site within 10 minutes of removing the MANTA sheath without need for manual or mechanical compression and without later rebleeding (trivial or subcutaneous oozing will not be considered bleeding; light finger pressure to control subcutaneous oozing will not be considered manual compression). Classification of success reported on Artery Assessment and Procedure eCRFs.

Subjects to include: All subjects with a procedure attempt will be included in this analysis.

Statistical analysis (both patient and device based): The time to hemostasis will be summarized using descriptive statistics including mean, standard deviation, median, interquartile range, minimum and maximum, and 95% confidence intervals will be calculated (device-based summary and patient-based using the longest time). Additionally, the proportion of subjects with hemostasis success will be summarized along with a 95% confidence interval (patient-based summary).

## 5.2 Safety Endpoint 1: VARC-2 Major Complications

Objective: To quantify the real-world VARC-2 major femoral vascular complication incidence using the MANTA device.

Endpoint: The percentage of patients with one or more VARC-2 Major femoral vascular complications as adapted from VARC-2 definitions within 30 days following procedure. The classification of "major" will be determined by the CEC and will be recorded in the CEC spreadsheet.

VARC-2 Major femoral vascular complication definition:

- Femoral access site or access-related vascular injury (dissection, stenosis, perforation, rupture, arterio-venous fistula, pseudoaneurysm, hematoma, irreversible nerve injury, compartment syndrome, percutaneous closure device failure) leading to death, life-threatening or major bleeding; OR,
- downstream distal embolization (lower extremities) requiring surgery or resulting in amputation; OR,
- the use of unplanned endovascular or surgical intervention associated with death, major femoral bleeding; OR,
- any new ipsilateral lower extremity ischemia documented by patient symptoms, physical exam, and/or decreased or absent blood flow on lower extremity angiogram; OR,
- surgery for femoral access site-related nerve injury; OR,
- permanent femoral access site-related nerve injury.

Subjects to include: All subjects with a procedure attempt will be included in this analysis.

Statistical analysis (patient based): The number of subjects, percentage of patients and 95% confidence intervals for the percentage of subjects will be calculated at a minimum for subjects experiencing any type of major complication as previously defined. Additional summaries may include splitting into adverse event type as collected via the case report forms.

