6.2. Minimization of bias

Potential for bias during this registry has been minimized by design of a well-controlled registry, expected conduct under the terms of an approved study protocol, use of specific device indications and contraindications per IFU, careful definitions for study procedures and outcomes and prospectively defined methods of data analysis.

6.3. *Randomization*

There is no randomization in this investigation.

6.4. *Subject Replacement*

Only patients who exit the study before device implantation will be replaced by new subjects. Up to 500 subjects will receive the MANTA vascular closure device. Patients that exit the study after implantation but before study completion will not be replaced by new patients.

6.5. *Study Population*

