6.5.4 Subject Withdrawal or Discontinuation

Subjects must be informed about their right to withdraw from the study at any time and for any reason without sanction, penalty, or loss of benefits to which the subject is otherwise entitled. Withdrawal from the study will not jeopardize their future medical care or relationship with the investigator. Subjects will be asked to specify the reason for their termination, but have the right not to answer.

The investigator may decide to withdraw a subject from the study at any time with reasonable rationale. The subject's future care will not be influenced by a decision, voluntary or otherwise, to withdraw from the study. All reasonable efforts should be made to retain the subject in the study until completion of the study.

Reasons for subject withdrawal include, but are not limited to:

- Subject withdraws consent
- Subject refuses to continue their participation
- Subject does not meet the inclusion/exclusion criteria
- Subject is deceased (event or symptoms pertaining to outcome of death must be documented on an Adverse Event CRF)
- Subject's participation is terminated by the investigator, although the subject consented, since participation is no longer medically appropriate
- Subject is „lost to follow up“ (subject does not adhere to the scheduled follow up visits but has not explicitly requested to be withdrawn from the study)
- Site personnel should make reasonable efforts to locate and communicate with the subject in order to achieve subject compliance to the scheduled follow up visits

If a subject withdraws from the study, the site will record the subject's reasons for withdrawal on the End of Study CRF.

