6.5.6 Duration of the Study

All enrolled subjects will be expected to complete the 30-Day Follow-Up visit. One hundred (100) to 120 subjects from up to 7 investigational sites will also, after informed consent is obtained, complete a 12M follow-up visit.

Anticipated Study Duration Timeline	
First Patient In	January 2018
Last Patient In	July 2019
Endpoint Analysis	October 2019
Study Close	September 2020

7. Study Procedures

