## 6 Data Conventions and Missing Data

No imputations will be made for missing data. All available data will be summarized for any summary provided the subject has a procedure attempt.

If an onset date for an AE is incomplete, every effort will be made by the clinical team to identify and collect a valid date from the site, but in case any are incomplete, then the following rules will be used:

- If the day of the month is missing, the first of the month will be used unless it precedes the procedure date. Then the procedure date will be used.
- If the month of missing the date of the procedure will be used.
- No year is expected to be missing as the follow-up is quite short.

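### The 30-day complication rates use all procedure attempts as denominator with no rule for subjects who exit before Day 30, so they can be biased low

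*SAP*

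**What the plan says.** SAP 5.2 defines the primary safety endpoint as "The percentage of patients with one or more VARC-2 Major femoral vascular complications as adapted from VARC-2 definitions within 30 days following procedure". It then sets the analysis population: "All subjects with a procedure attempt will be included in this analysis". SAP 5.3 applies the same population to the minor complication rate, counting a minor complication only in subjects without a major one. Both rates are to be reported as a count, a percentage and a 95% confidence interval.

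SAP 6 has two sentences on missing data: "No imputations will be made for missing data" and "All available data will be summarized for any summary provided the subject has a procedure attempt". It does not say whether an unknown Day-30 status is available data. The only specific rules that follow are for incomplete adverse event onset dates.

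The protocol foresees incomplete follow-up. Section 6.5.6 says "All enrolled subjects will be expected to complete the 30-Day Follow-Up visit". Section 6.5.4 lists withdrawal, death and loss to follow-up among the reasons for exit, and defines a lost subject as one where the "subject does not adhere to the scheduled follow up visits but has not explicitly requested to be withdrawn from the study". Section 6.4 adds "Patients that exit the study after implantation but before study completion will not be replaced by new patients".

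SAP 5 will compare the 95% confidence intervals with published rates. A published rate inside the interval will be reported as no demonstrated difference.

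**The concern.** A subject who exits on, say, Day 5 with no event reported is in the denominator and cannot enter the numerator. In effect that subject is assigned the favourable outcome for Days 6 to 30, which is hard to square with a statement that nothing is imputed. If SAP 6 is instead meant to drop subjects of unknown Day-30 status, it conflicts with the population stated in 5.2 and 5.3. Two programmers could follow the same text to different denominators.

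One component of the major endpoint shows the difficulty directly. SAP Appendix 1 and Protocol section 4 define permanent nerve injury as lasting more than 30 days, which cannot be established in a subject last seen before then. Nor does the SAP say how death before Day 30 without a complication enters the rate.

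Unobserved events can only lower the major rate. At stake are the primary safety estimate, the secondary one, and the interval set against the literature.

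**Working it through.** **Inputs from the documents.** Up to 500 subjects (SAP 4, which adds "There is no statistical basis for the sample size"). As illustrative true rates, the weighted averages in SAP Table 3: major 4.2%, minor 11.5%. Weighting the 14 rows by N reproduces these: total N = 2659, major 4.22%, minor 11.53%.

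**Assumptions, not in the documents.** Share lost before Day 30, d, from 0 to 10%. Share of the lost subjects' events that fall after loss, f, from 0.25 to 1. Loss unrelated to outcome. Exact (Clopper-Pearson) intervals, since the SAP names no method. The plan states no attrition figure, so there is none to reproduce.

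**Step 1: bias of the literal rule.** Events before exit still count and those after exit are missed, so with true risk p the expected rate is p × (1 − d × f) and the bias is −p × d × f.

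| Endpoint | d | f = 0.25 | f = 1 |
|---|---|---|---|
| Major, p = 4.2% | 2% | −0.02 | −0.08 |
| | 5% | −0.05 | −0.21 |
| | 10% | −0.11 | −0.42 |
| Minor, p = 11.5% | 2% | −0.06 | −0.23 |
| | 5% | −0.14 | −0.58 |
| | 10% | −0.29 | −1.15 |

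Entries are percentage points. For example, 4.2 × 0.10 × 0.25 = 0.105. For scale, 21/500 = 4.20% has a 95% interval of 2.62 to 6.35%, about −1.6 to +2.2 points. For the minor rate there is a small opposite effect that the formula ignores: a subject with a minor event who is lost before a major one stays in the minor count.

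**Step 2: the obvious alternative, removing event-free lost subjects.** With 21 events observed:

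- 5% lost: 21/475 = 4.42% (2.76 to 6.68%)
- 10% lost: 21/450 = 4.67% (2.91 to 7.05%)

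This keeps early events in subjects later lost but removes their event-free counterparts. Its expected value is p(1 − df) / [(1 − d) + d × p × (1 − f)]. At d = 10% and f = 0.25 that is 0.04095 / (0.90 + 0.00315) = 4.53%, which is 0.33 points too high. The literal rule gives 4.095%, about 0.11 points too low. The alternative is unbiased only at f = 1 and is the worse of the two when f is below about 0.5.

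**Step 3: loss related to outcome.** Step 1 does not bound this case. If every lost subject had a major event, the rate would be (21 + L)/500 for L lost: 6.2% for 10, 9.2% for 25 and 14.2% for 50. This is an extreme limit, not an expectation.

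**Step 4: could the literature statement change?** With the Step 2 denominator the upper limit passes 6.9% at 41 lost (6.91%) and 7% at 48 lost (7.01%). Those are the major rates of two Table 3 rows (N = 203 and N = 111). At 25 lost neither is reached. Because that denominator overcorrects when events are early, these counts show only that substantial loss would be needed.

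**The case against.** The strongest reply is that the SAP never says lost subjects are event-free. Sections 5.2 and 5.3 name an analysis set, and SAP 6 can be read as leaving unknown Day-30 status out of the percentage. That stands: the event-free count is the literal consequence of the text, not a stated rule. The rule still needs writing down, because the other reading contradicts the stated population.

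A reader might go further and infer that the reported rates are biased low. The documents do not support that. They give no loss rate, and the bias is zero if nobody is lost or if those lost had no later event. Nor may the outcome-unrelated figures be taken as an upper limit, as Step 3 shows.

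On size, the effect is small beside the sampling error, and the study is descriptive with no hypothesis test (Protocol 8.1). Major events also appear to be early: in the EU pre-market study the three subjects with major complications were the three without hemostasis success (Protocol section 1.4). Both points stand and limit the importance of the issue.

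Safeguards exist. Sites must make reasonable efforts to reach subjects, the synopsis allows 30-day follow-up by phone in some circumstances, and SAP 5.5 tabulates average follow-up, type of follow-up and exit reasons. These make loss visible but do not change the rate or its interval.

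Finally, comparability favours the crude rate. The EU pre-market benchmark is 3/50 over all treated subjects, although 4 of the 50 died during that 60-day study. This is a good reason to keep the all-attempts percentage in the table.

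**Conclusion.** The point holds as a gap in specification with a possible downward bias. The SAP does not define how subjects without complete 30-day follow-up are counted, and the literal rule treats those who exit without an event as event-free while declaring that nothing is imputed.

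For the major rate, the understatement is at most about 0.4 points and about 0.1 points when a quarter of the lost subjects' events come after loss. For the minor rate the corresponding figures are about 1.2 and 0.3 points. These rest on 500 subjects, true rates of 4.2% and 11.5%, and up to 10% loss unrelated to outcome; the last is an assumption. If loss is related to outcome, the error could be larger. This is a worthwhile improvement, not a threat to the study's conclusions.

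**What to change.** In SAP 5.2 and 5.3, keep the percentage of all procedure attempts and state explicitly how exits and deaths before Day 30 are counted in it. Beside it, report the Day-30 cumulative incidence for each endpoint (Aalen-Johansen estimator, censoring at last contact, death as a competing event) with its 95% confidence interval. For the minor rate, a major complication must also be treated as a competing outcome, because SAP 5.3 counts minor complications only in subjects without a major one. Use the cumulative-incidence interval in the literature comparison of SAP 5.

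Report the number of subjects with 30-day follow-up, an earlier endpoint event, or death, so that the number of unknown status is plain. Do not make an evaluable-only denominator the main result. The estimator still assumes that loss is unrelated to outcome, so the (events + lost)/N limit is worth a footnote if loss turns out appreciable.

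The cost is SAP wording and a little programming, using onset, exit and death dates already collected. The SAP records that follow-up was still being completed when it was drafted. The downside is a slightly less favourable rate, and a measure that differs slightly from the crude percentages in the pre-market benchmarks. That is why the crude rate stays alongside.

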## 5.3 Safety Endpoint 2: VARC-2 Minor Complication

Objective: To quantify the real-world VARC-2 minor femoral vascular complication incidence using the MANTA device.

Endpoint: The percentage of patients with one or more VARC-2 Minor femoral vascular complications (and no major VARC-2 complications) as adapted from VARC-2 definitions within 30 days following procedure.

Minor femoral vascular complication definition:

- Access site or access-related vascular injury (dissection, stenosis, perforation, rupture, arterio-venous fistula, pseudoaneuysms, hematomas, percutaneous closure device failure) not leading to death, life-threatening or major bleeding; OR,
- downstream distal embolization (lower extremities) treated with embolectomy and/or thrombectomy and not resulting in amputation; OR,
- any unplanned endovascular stenting or unplanned surgical intervention not meeting the criteria for a major vascular complication; OR,

- vascular repair or the need for vascular repair (via surgery, ultrasound guided compression, transcatheter embolization, or stent-graft); OR,
- percutaneous closure device failure\*.

\*Failure of a closure device to achieve hemostasis at the arteriotomy site leading to alternative treatment (other than manual compression or adjunctive endovascular ballooning).

Subjects to include: All subjects with a procedure attempt will be included in this analysis.

Statistical analysis (patient based): The number of subjects, percentage of patients and 95% confidence intervals for the percentage of subjects will be calculated at a minimum for subjects experiencing any type of minor complication as previously defined. Additional summaries may include splitting into adverse event type as collected via the case report forms.

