The following is a suggested, but not required, method for managing arterial bleeding: If hemostasis is not immediate upon deployment, apply manual pressure and check the access site for hemostasis at approximately one minute increments following sheath withdrawal through

10 minutes, and then at approximately two-minute intervals through 20 minutes, until hemostasis. If hemostasis is not achieved by 20 minutes, the access site should be managed per medical judgment inclusive of use of a contralateral balloon or mechanical compression device. A checking interval of 5 minutes is recommended in these cases if deemed medically appropriate.

Treatment of Oozing/Continued Bleeding

- Oozing that is controllable with compression bandages, sand bags or light manual pressure is subcutaneous in origin. Light manual compression may be substituted with light compression applied by a mechanical compression device.
- Bleeding which is not controlled by light manual compression should be controlled by compression of the femoral artery via mechanical or manual compression.
- If necessary, balloon occlusion from the contralateral access site may be performed; such balloon occlusion will not be considered an unplanned intervention.
- Failing these steps, rescue measures may include placement of a stent-graft at the access site or surgical intervention.

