### 3 Clinical Events Committee

An independent Clinical Events Committee (CEC) will be established for this study. The CEC will include members qualified to review adverse event data for this study. During the CEC review, a designated CEC member is responsible for reviewing the documentation for events that occurred in their country. If complex events emerge, the designated CEC member can ask the CEC Chair to convene a conference call to discuss the specific event(s). The CEC will be established and operate according to a charter defined prior to the initiation of the trial. The CEC will review individual adverse events that meet the following criteria:

- AEs that are considered by the investigator to be definitely, probably or possibly device related will be adjudicated by CEC parallel to enrollment. Additionally, outcomes not associated with the MANTA device may also be adjudicated by CEC.

The primary responsibilities of the CEC over the course of the study are to review and refine serious adverse event definitions, and to review and adjudicate serious adverse events.

The CEC will determine if each reviewed adverse event meets the definition of a VARC-2 Major femoral vascular complication or a VARC-2 Minor femoral vascular complication or neither definition. For each AE reviewed, the CEC may also adjudicate its device-relatedness. Any analysis of the primary and secondary safety endpoints will be based on CEC-adjudicated data.

Specifically, the CEC will review:

- Any adverse events that are possibly, probably or definitely related to the MANTA device. The CEC members will adjudicate whether each event is a VARC-2 Major or Minor Femoral Vascular Complications within 30 days following procedure or whether it is no-event (does not meet either definition). determine the percentage of subjects with one or more VARC-2 Major or Minor Femoral Vascular Complications within 30 days following procedure.

The following events below will not be submitted for adjudication as these events do not meet the definitions of VARC-2 Major/Minor vascular complications or definitions in the MARVEL Protocol PSD-212.

- Hematoma: less than 2 cm in size or no size is recorded for the hematoma and it requires no treatment or requires only prolonged/adjunctive compression.

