  - Rationale: Per MARVEL Protocol PSD-212, a hematoma is defined as an expanding or non-expanding subcutaneous mass of blood greater than 2 cm in its longest axis, confirmed by ultrasound, and VARC-2 excludes percutaneous closure device failure requiring only manual compression from minor vascular complications.
- Minor Bleeding: requiring no treatment or requiring only prolonged/adjunctive compression.
  - Rationale: Per VACR-2 criteria, minor bleeding requiring adjunctive compression is not categorized as a VARC-2 major/minor vascular complication and percutaneous closure device failure requiring only manual compression is excluded from minor vascular complications.

The CEC member will provide the following assignments for each AE:

- If AE resulted in death, classify death:

- Cardiac
    - Non-cardiovascular
    - Vascular
  - If AE resulted in bleeding complications: (yes/no)
    - If yes, define event type below:
      - BARC 0
      - BARC 1
      - BARC 2
      - BARC 3a
      - BARC 3b
      - BARC 3c
      - BARC 4
      - BARC 5a
      - BARC 5b
  - VARC-2 Major Complication (yes/no)
    - Type of classification (from drop down list)
  - VARC-2 Minor Complication (yes/no)
    - Type of classification (from drop down list)
  - Device relatedness
    - Not related
    - Unknown
    - Possible
    - Probably
    - Definite
  - Procedure relatedness
    - Not related
    - Unknown
    - Possible
    - Probably
    - Definite

The CEC adjudications will be documented in a controlled limited access Excel spreadsheet.

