## 7 Appendix 1: Definitions from the protocol

**Adjunctive Compression:** Compression methods (including sand bags, compression bandages, and light manual pressure) for controlling cutaneous or subcutaneous oozing.

**Adverse Device Effect (ADE):** Adverse event (see definition below) resulting from insufficient or inadequate instructions for use, deployment, implantation, installation, or operation, or any malfunction of the investigational medical device. This definition includes any event resulting from use error or from intentional misuse of the investigational medical device.

**Adverse Event (AE):** Any untoward medical occurrence, unintended disease or injury, or untoward clinical signs (including abnormal laboratory findings) in subjects, users or other persons, whether or not related to the medical device. This definition includes events related to the procedures involved. For users or other persons, this definition is restricted to events related to devices.

**Cachexia:** Defined as very thin, or body mass index <20 kg/m^2.

**Device Deficiency:** Inadequacy of a medical device with respect to its identity, quality, durability, reliability, safety or performance; includes device malfunctions, use errors and inadequate labeling

**Eccymosis:** An area of subcutaneous discoloration caused by the extravasation of blood into the subcutaneous tissue not associated with a definable, palpable subcutaneous mass.

**Hematoma:** An expanding or non-expanding subcutaneous mass of blood greater than 2 cm in its longest axis, confirmed by ultrasound.

**Hemostasis Success:** Hemostasis at the puncture site within 10 minutes of removing the MANTA sheath without need for manual or mechanical compression and without later rebleeding (trivial or subcutaneous oozing will not be considered bleeding; light finger pressure to control subcutaneous oozing will not be considered manual compression).

**Major and Minor Access Site Related Complications (as described below):** within 30 days of procedure. Adapted from the VARC-2 Clinical Guidelines [3]

**Major femoral vascular complications:** Composite endpoint that includes any of the following adverse events:

- Femoral access site or access-related vascular injury (dissection, stenosis, perforation, rupture, arterio-venous fistula, pseudoaneurysm, hematoma, irreversible nerve injury, compartment syndrome, percutaneous closure device failure) leading to death, lifethreatening or major bleeding; OR,

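### SAP 3 can withhold from the CEC a compression-only closure failure that the SAP 5.3 footnote counts as Minor; the effect on the Minor rate is unknown

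*SAP*

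**What the plan says.** **The definition.** The Minor list in SAP 5.3 includes percutaneous closure device failure. Its footnote defines this as failure to achieve hemostasis "leading to alternative treatment (other than manual compression or adjunctive endovascular ballooning"). The same footnote stands in Protocol 4 and SAP Appendix 1. Two treatments are exempt: manual compression and ballooning.

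**The filter.** SAP 3 lists events that will not go to the CEC because, it says, they do not meet the Major or Minor definitions. One category is "Minor Bleeding: requiring no treatment or requiring only prolonged/adjunctive compression". The other is hematoma under 2 cm, or with no recorded size, under the same treatment condition. The reason given for the bleeding category is that "percutaneous closure device failure requiring only manual compression is excluded from minor vascular complications"; the hematoma category gives a similar reason.

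**The terms.** Protocol 4 and SAP Appendix 1 define adjunctive compression as "Compression methods (including sand bags, compression bandages, and light manual pressure) for controlling cutaneous or subcutaneous oozing". Neither document defines *prolonged*.

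**The route to the endpoint.** SAP 3 also says that the CEC will review "Any adverse events that are possibly, probably or definitely related to the MANTA device", and that "Any analysis of the primary and secondary safety endpoints will be based on CEC-adjudicated data".

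**Other mentions of compression.** Protocol 7.5 says that bleeding beyond the reach of light manual compression "should be controlled by compression of the femoral artery via mechanical or manual compression". Hemostasis Success (SAP 5.1) requires hemostasis "without need for manual or mechanical compression".

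**The concern.** SAP 3 justifies its filter by saying that the withheld events fall outside the definitions. For events managed by manual compression, the footnote supports that. For a closure failure managed only by a mechanical compression device, beyond light pressure for oozing, it does not: the footnote leaves mechanical compression among the alternative treatments that make the failure Minor.

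The omission is hard to read as shorthand. Hemostasis Success and Protocol 7.5 both name manual and mechanical compression when they mean both.

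A withheld event cannot enter the endpoint, since only adjudicated events count. At stake is an undercount in the secondary safety endpoint that depends on which AE term a site chose and how the filter was read. SAP 5 prespecifies what will be reported when a literature rate lies inside the 95% confidence interval, so a modest change in the count can change that statement.

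**Working it through.** **1. Tracing one case.** Take arterial bleeding after MANTA deployment, stopped by compression alone, with no Major complication.

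| Treatment and AE term | Footnote, SAP 5.3 | Filter, SAP 3 | Counted as Minor? |
|---|---|---|---|
| Manual, either term | Exempt | Rationale fits | No |
| Mechanical (not light), reported as closure failure | Minor | Not a withheld category; reviewed if possibly, probably or definitely device-related | Yes, if the CEC applies the footnote |
| Mechanical (not light), reported as minor bleeding, filter read as any compression | Minor | Withheld | No |
| Mechanical (not light), reported as minor bleeding, filter read as manual or light only | Minor | Submitted if device-related as above | Yes, if the CEC applies the footnote |

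The definition and the filter conflict in the third row.

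The table uses the SAP 5.3 list. Protocol 4 and SAP Appendix 1 add a last Minor item for any other AE definitely or probably related to the device or access site. SAP 5.3 omits it. If it applies, even the manual case could be Minor.

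**2. The only related rate in the documents.** Protocol 1.4, EU pre-market study:
- Hemostasis Success was 47/50 = 94.0%, so failures were 3/50 = 6.0% (exact 95% CI 1.3% to 16.6%). The time categories add up: 37 + 10 + 3 = 50.
- All three failures had manual pressure, so reported mechanical use is 0 of 3 (exact 95% CI 0% to 71%, which tells us almost nothing).
- All three were Major under that study's own definition. SAP Table 2 lists 1/50 as VARC-2 Major, so at least two of the three were not VARC-2 Major.

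**3. Possible shift in the Minor rate.** Shift = f × m × k, where
- f = hemostasis-failure rate, taken as 6%;
- m = share of failures treated by mechanical compression only (assumed; not in the documents);
- k = share of failures that are not VARC-2 Major (assumed; 2/3 if Table 2 is the guide). It is needed because SAP 5.3 counts a patient as Minor only if there is no Major complication.

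At N = 500, f gives 500 × 0.06 = 30 failures.

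| m | k | Patients | Shift (points) |
|---|---|---|---|
| 0 | any | 0 | 0 |
| 0.10 | 1 | 3 | 0.6 |
| 0.25 | 1 | 7.5 | 1.5 |
| 0.50 | 0.5 | 7.5 | 1.5 |
| 0.50 | 1 | 15 | 3.0 |
| 1 | 2/3 | 20 | 4.0 |
| 1 | 1 | 30 | 6.0 |

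These figures also suppose that every such case is withheld under one reading and counted under the other, so each is an upper value for its m and k.

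**4. What would change a reported statement.** Exact (Clopper-Pearson) intervals against the US Minor rate of 2.7% in Table 2, from an illustrative starting count of 14:
- 14/500 = 2.8%, CI 1.5% to 4.7%: contains 2.7%.
- 21/500 = 4.2%, CI 2.6% to 6.3%: still contains it.
- 22/500 = 4.4%, CI 2.8% to 6.6%: excludes it.

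The difference is 22 − 14 = 8 patients, or 8/500 = 1.6 points. That is 8/30 = 27% of the failures expected at 6%.

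**The case against.** The best defence is that SAP 3, read with its own definitions, does not reach these cases. Adjunctive compression is a defined term for oozing, the rationale speaks only of manual compression, and closure device failure is not a withheld category. Failed hemostasis is a listed potential effect in Protocol 9.2, and device-related AEs go to the CEC. On that reading a mechanical-compression failure is lost only if the site calls it minor bleeding and the filter is then applied broadly. This is right as far as it goes, and it limits the point to that route. It does not close the route: *prolonged* is undefined, and the filter as written names no method.

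A reader might infer three stronger claims that the documents do not support.
- *Identical bleeds score differently by hand or device.* If the filter covers both methods, both cases score as no event; the conflict is then between definition and filter. Protocol 7.5 does not help this claim, because it is procedural guidance and scores nothing. Its suggested sequence starts with manual pressure and mentions a device when hemostasis is not reached by 20 minutes, so a device may mark a longer bleed.
- *The Minor rate moves by several points.* No document gives a mechanical-compression rate, and the three EU failures had none reported. The larger figures are assumed ceilings, and the range starts at zero.
- *The rate is biased low against Tables 2 and 3.* That would require knowing how the reference studies scored compression, which the documents do not say.

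It is also fair that Hemostasis Success counts both methods as failure, that the listings of MANTA-related AEs describe treatments, and that comparison with the literature is descriptive. These make some cases visible but do not put a withheld event into the Minor rate.

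**Conclusion.** The point holds in a limited form. The SAP 3 filter is wider than its own rationale and than the footnote it relies on. A closure failure treated only by non-light mechanical compression can meet the written Minor definition and still be left out before adjudication, depending on the AE term and on how the filter is read.

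The size cannot be established. Assuming the EU 6% failure rate carries over to 500 patients, the shift lies between 0 and about 4 points with two-thirds of failures non-Major, or 6 points with all non-Major. The upper ends require every failure to be managed by mechanical compression only. The eight-patient example shows that a shift well below those ceilings could alter a prespecified comparison; it is not a forecast.

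This should be corrected because it is a stated rule that can undercount a secondary safety endpoint. It concerns endpoint scoring only and implies nothing about how bleeding should be managed.

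**What to change.** 1. In SAP 3, limit both withheld categories (bleeding and hematoma) to events needing no treatment, manual compression only, or light adjunctive compression for oozing. Define *prolonged*.
2. Submit to the CEC every closure failure or bleed at a MANTA site treated with non-light mechanical compression, whatever AE term the site used.
3. Reconcile this with the last Minor item in Protocol 4 and SAP Appendix 1, which SAP 5.3 omits, so that one list decides how compression-only events are scored.
4. Optionally, add one row giving the Minor rate without patients whose only extra treatment was mechanical compression.

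The cost is SAP wording, some additional CEC reviews and, if wanted, one table row. The reported Minor rate may be slightly higher. The number of extra reviews is not known. Enrollment had closed when the SAP was drafted and adjudication ran alongside it, so events already screened out would have to be rechecked. The documents do not show compression method as a separate CRF field, so these cases may have to be found from the treatment descriptions in the AE data.
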